3. PATIENT SELECTION

3.1 Inclusion Criteria (all of the following criteria must be met for enrollment)

3.1.1 Patients must have one of the following, histologically or cytologically confirmed:

- AML (non- acute promyelocytic leukemia [APL] AML)
 - AML that is relapsed or refractory to at least one prior line of therapy
- MDS, must meet all of the following at the time of enrollment:
 - Higher risk MDS (intermediate-2 or high risk by the original IPSS) (Greenberg *et al.*, 1997), and
 - Relapsed, refractory, or intolerant to at least one prior line of therapy containing a hypomethylating agent (DNA methyltransferase inhibitor).

3.1.2 Age ≥ 18 years.

Because no dosing or adverse event data are currently available on the use of MLN4924 (pevonedistat) in combination with belinostat in patients < 18 years of age, children are excluded from this study, but will be eligible for future pediatric trials.

3.1.3 ECOG performance status ≤ 2 (Karnofsky $\geq 60\%$, see Appendix A).

3.1.4 Patients must have adequate organ and marrow function as defined below:

- | | |
|--|---|
| – total bilirubin | \leq upper limit of normal (ULN) for the laboratory except in patients with Gilbert's syndrome. Patients with Gilbert's syndrome may enroll if direct bilirubin $\leq 1.5 \times$ ULN for the laboratory of the direct bilirubin. |
| – AST(SGOT)/ALT(SGPT) | $\leq 3 \times$ institutional ULN. |
| – creatinine clearance | Within normal limits for the laboratory |
| OR | |
| – estimated glomerular filtration rate (GFR) | ≥ 60 mL/min/1.73 m ² appropriate to race for patients |

with creatinine levels above institutional normal.

- 3.1.5 Known human immunodeficiency virus (HIV) positive patients who meet the following criteria will be considered eligible:
- CD4 count >350 cells/mm³
 - Undetectable viral load
 - Maintained on modern therapeutic regimens utilizing non-CYP-interactive agents
 - No history of Acquired Immune Deficiency Syndrome (AIDS)-defining opportunistic infections
- 3.1.6 If evidence of chronic hepatitis B virus (HBV) infection, HBV viral load must be undetectable on suppressive therapy, if indicated.
- 3.1.7 If history of hepatitis C virus (HCV) infection, patients must be treated and have an undetectable HCV viral load.

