11. STUDY CALENDAR

Unless stated otherwise, baseline evaluations are to be conducted within 1 week prior to start of protocol therapy. Bone marrow evaluations for disease assessment must be done ≤ 3 weeks prior to start of therapy. Scans and X-rays must be done ≤ 2 weeks prior to the start of therapy. Hepatitis serologies and left ventricular ejection fraction assessment should be done ≤ 4 weeks prior to the start of therapy. In the event that the patient's condition is deteriorating, laboratory evaluations should be repeated within 48 hrs prior to initiation of the next cycle of therapy.

Study Calendar

	Baseline ^{a,b,t}	Cycle 1						Subsequent Cycles						End of Treatment ^c	End of 30-Day Safety Follow-up ^d	Extended Follow-up ^{d,e}		
		Day 1	Day 2	Day 3	Day 4	Day 5	Day 8	Day 15	Day 1	Day 2	Day 3	Day 4	Day 5				Day 8	Day 15
MLN4924 (pevonedistat)		A		A		A			A		A		A					
Belinostat		B	B	B	B	B			B	B	B	B	B					
Performance status	X																	
LVEF assessment by echocardiogram or radionuclide angiography	X ^r																	
History and physical exam and weight.	X	X ^a							X ^a							X		
Urinalysis ^f	X																	
Informed consent	X																	
Vital signs (T, P, R, BP, pulse oximetry)	X	X		X		X			X		X		X			X		
Height	X																	
Demographics	X																	
Concurrent medications ^g	X	X ^a							X ^a							X		
Baseline symptoms and conditions	X																	
AE assessment		X-----X													X	X		
CBC, differential, platelet count	X	X		X		X	X	X	X ^a							X		
Basic metabolic panel ^h , eGFR	X	X	X	X		X	X	X	X ^a		X ^a		X ^a		X			
Uric acid, Mg ²⁺	X	X	X	X		X	X	X	X ^a						X			
PT/INR, PTT	X	X				X	X	X	X ^a									
Hepatic panel ^{i,j}	X	X		X		X	X	X	X ^a		X ^a		X ^a		X			
LDH, PO ₄	X	X	X	X														
CD4; HIV viral load ^u	X																	
Hepatitis serologies (Hep B SAg, Hep B S Ab, Hep B c Ab; Hep B viral load) ^{k,v}	X																	

	Baseline ^{a,b,t}	Cycle 1							Subsequent Cycles							End of Treatment ^c	End of 30-Day Safety Follow-up ^d	Extended Follow-up ^{d,e}
		Day 1	Day 2	Day 3	Day 4	Day 5	Day 8	Day 15	Day 1	Day 2	Day 3	Day 4	Day 5	Day 8	Day 15			
Hepatitis C viral load ^v	X																	
ECG	X				X ^l													
Serum or urine pregnancy test	X	X ^{a,m}							X ^{a,m}									
Disease assessment ^{n,s}	X ^s	Every two cycles																
Reported clinical status																		X
Blood for PK studies		X ^o																
Blood or bone marrow aspirate for PD studies ^p	X	X																

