																		

- A. MLN4924 (pevonedistat): Dose as assigned; IV over 60 minutes (\pm 10 minutes) once daily (QD) on Days 1, 3, and 5 of each 21-day cycle. When both drugs are given on the same day (Days 1, 3, 5), start the MLN4924 (pevonedistat) infusion within 60 mins after the completion of belinostat infusion.
- B. Belinostat: Dose as assigned; IV over 30 minutes QD on Days 1-5 of each 21-day cycle. Infusion may be extended to 3 hours pending patient tolerance.
- Prior to treatment
 - Unless stated otherwise, baseline evaluations are to be conducted within 1 week prior to start of study therapy. Repeat if not within 1 week prior to Cycle 1, Day 1. In the event that the patient's condition is deteriorating, laboratory evaluations should be repeated within 48 hrs prior to initiation of the next cycle of therapy.
 - End of treatment visit occurs after completion of all study treatment.
 - See Section 6.8.
 - Only for patients with a CR, CRi, CRc, CRm, ML-FS, PR, or SD, capture reported clinical status approximately every 2 months for 2 years following end of safety follow-up until disease progression or death. See Section 6.8.
 - Urinalysis to include turbidity and color, pH, specific gravity, protein, ketones, bilirubin, occult blood, nitrite, glucose, and leukocyte esterase. Microscopic analysis should be done at the discretion of the treating physician.
 - Include over-the-counter medications.
 - Sodium, potassium, carbon dioxide content, chloride, creatinine, blood urea nitrogen (BUN), glucose and calcium.
 - Alkaline phosphatase, ALT, AST and total bilirubin assessments must be performed and read prior to each dose of MLN4924 (pevonedistat).
 - Total bilirubin, direct bilirubin, ALP (alkaline phosphatase), AST, ALT, total protein, albumin.
 - Hepatitis serologies and, if needed, HBV viral load testing are to be done \leq 4 weeks prior to the start of therapy. HBV viral load only necessary if patients are Hepatitis B Ab positive.
 - Pre- & post-treatment on Cycle 1 Day 4 and whenever clinically indicated. Patients with risk factors for QT prolongation including CHF, bradyarrhythmias, electrolyte abnormalities or those on other drugs known to prolong the QT/QTc interval, such as Class Ia and III anti-arrhythmics, should be closely monitored as clinically indicated with ECGs and serum electrolytes (magnesium, potassium) while on study treatment. See Section 6.5.

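### As written, the renal criterion in 3.1.4 can exclude patients with better renal function and admit patients with worse

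*Combined protocol and SAP*

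**What the plan says.** The heading of protocol Section 3.1 makes every inclusion criterion mandatory, and Section 4.3.1 has sites verify that all of them are met before registering a patient. Section 3.1.4 sets the renal requirement as two branches joined by OR:

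- Branch 1: "creatinine clearance", with the limit "Within normal limits for the laboratory". No number is given.
- Branch 2: estimated GFR "≥ 60 mL/min/1.73 m"², appropriate to race, for patients "with creatinine levels above institutional normal".

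The baseline column of the Section 11 calendar has a row for the "Basic metabolic panel" together with eGFR. Footnote h defines the panel as "Sodium, potassium, carbon dioxide content, chloride, creatinine, blood urea nitrogen (BUN), glucose and calcium". The calendar has no row for creatinine clearance, and the protocol names no formula or urine collection for it.

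**The concern.** Branch 1 is open to everyone, but branch 2 is closed to patients whose creatinine is normal. Those patients must meet the laboratory's normal range for clearance. A patient whose creatinine is already raised may instead use a fixed floor of 60. If the laboratory's lower limit is above that floor, the stricter test falls on the group with the better creatinine.

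The criterion is there to ensure adequate organ function, and renal function matters for this regimen: Section 2.2.2.2 lists renal failure and elevated creatinine among the dose-limiting toxicities of earlier pevonedistat studies. A rule that can run backwards does that job poorly. It also invites different readings across participating sites. A literal reader turns away some patients with normal creatinine, and a reader who assumes that the eGFR route was meant for all registers patients who do not meet the text.

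**Working it through.** The plan states no figure to reproduce, so the check is of the rule's logic.

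**Inputs from the documents.** From 3.1.4: the two branches, the OR, the eGFR floor of 60, and the restriction of branch 2 to raised creatinine.

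**Assumptions.** L, the laboratory's lower limit of normal clearance, is not in the documents and is varied from 60 to 100 mL/min. Clearance and eGFR are treated as numerically equal (call the value g), although one is unindexed and the other is indexed to body surface. The upper end of the normal range is ignored.

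**Rule as written.** Eligible if g ≥ L, or if creatinine is raised and g ≥ 60.

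- Normal creatinine: excluded for every g below L.
- Raised creatinine: admitted for every g from 60.

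In whole units, the largest gap between an excluded patient with normal creatinine and an admitted patient with raised creatinine is (L − 1) − 60:

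| Assumed L | Normal creatinine excluded up to | Raised creatinine admitted from | Largest gap |
|---|---|---|---|
| 60 | 59 | 60 | none |
| 70 | 69 | 60 | 9 |
| 80 | 79 | 60 | 19 |
| 90 | 89 | 60 | 29 |
| 100 | 99 | 60 | 39 |

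**Does the inversion survive the difference in measures?** Take a 70-year-old, 75 kg man and assume an upper limit of normal creatinine of 1.2 mg/dL. Clearance is by Cockcroft-Gault and eGFR by CKD-EPI 2021; both formulas are assumptions, since the protocol names neither.

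- Creatinine 1.0 (normal): clearance = (140 − 70) × 75 / (72 × 1.0) = 72.9; eGFR = 142 × (1.0/0.9)^−1.2 × 0.9938^70 = 81.0. Branch 2 is closed to him, so he is excluded for any L above 72.9.
- Creatinine 1.25 (raised): clearance = (70 × 75) / (72 × 1.25) = 58.3; eGFR = 142 × (1.25/0.9)^−1.2 × 0.9938^70 = 61.9. Branch 2 is open to him, so he is eligible.

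At the higher creatinine he is worse on both measures, yet that is where he is admitted. At L = 70 he would qualify in both states, so this example also depends on L.

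**Possible repair A: open the eGFR branch to all.** Eligible if g ≥ L or g ≥ 60. The lowest admitted value is 60 in both creatinine groups for every L in the table. On the same simplification, the inversion is gone.

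**Possible repair B: replace creatinine clearance with serum creatinine in branch 1.** Keep the same assumed upper limit of 1.2 and the same formulas.

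- An 80-year-old, 50 kg woman with creatinine 1.0: clearance = (140 − 80) × 50 / (72 × 1.0) × 0.85 = 35.4; eGFR = 142 × (1.0/0.7)^−1.2 × 0.9938^80 × 1.012 = 57.0. Admitted, because her creatinine is normal.
- A 70-year-old man with creatinine 1.3: eGFR = 142 × (1.3/0.9)^−1.2 × 0.9938^70 = 59.1. Excluded.

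Repair B leaves patients with normal creatinine with no filtration floor and produces a new inversion.

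**The case against.** The strongest reply is that the inversion is conditional. The protocol gives no lower limit for clearance, and a laboratory with a limit of 60, or a low age-adjusted one, shows none. That stands: the rule can run backwards, but the documents do not show that it does so at every site.

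A second reply is that the branches use different measures, and that the protocol asks for an eGFR appropriate to race whereas the formula used above has no race term. That makes the sizes approximate. It does not remove the problem, because the example patient is worse on both measures when he is admitted.

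Third, a missing calendar row does not make clearance unobtainable: it can be calculated from age, weight and creatinine, all of which are collected at baseline. That also stands. The calendar shows only that 3.1.4 and the schedule name different measures.

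A reader might infer three stronger things. One is that branch 1 is simply a slip for serum creatinine. The wording of branch 2 and the calendar make that plausible, but nothing in the documents confirms it, and the substitution fails the check above. Another is that many patients are affected because older patients predominate in AML. Section 2.1 supports the age distribution but gives nothing on how many have normal creatinine with reduced clearance. The third is that accrual will be slower, for which the documents offer no figure.

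**Conclusion.** The point holds in conditional form. No other part of the protocol opens the eGFR route to patients with normal creatinine, so 3.1.4 as written can exclude better renal function and admit worse whenever the laboratory's lower limit for clearance is above 60. The size is the band from 60 up to that limit, as tabulated, and it rests on treating clearance and eGFR as comparable and on a limit that the documents do not state. The consequence is an eligibility rule that may be applied differently between sites. The dose-limiting toxicity definition (6.2), the escalation rule (6.3) and the sample size (9.2) are unaffected.

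**What to change.** Reconcile the two branches of 3.1.4 with each other and with the Section 11 calendar, so that eligibility does not run backwards with renal function. One way is to delete the restriction of the eGFR branch to patients with raised creatinine, so that the existing eGFR criterion applies to everyone. The authors should confirm which measure they intend. If creatinine clearance stays, name how it is obtained and list it in the calendar. Do not merely replace it with serum creatinine.

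The cost is a one-line eligibility amendment. Opening the eGFR branch needs no new test and no new threshold, because eGFR is already scheduled at baseline.

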3.2 Exclusion Criteria (none of the following may be present for enrollment)

- 3.2.1 Clinical picture indicative of leukostasis or evidence of disseminated intravascular coagulopathy.
- 3.2.2 Uncontrolled coagulopathy or bleeding disorder.
- 3.2.3 Systemic antineoplastic therapy or radiotherapy for other malignant conditions within 14 days before the first dose of any study drug, except for hydroxyurea.
- 3.2.4 Uncontrolled high blood pressure (*i.e.*, systolic blood pressure >180 mm Hg, diastolic blood pressure >95 mm Hg).

- 3.2.5 Female patients who intend to donate eggs (ova) during the course of this study or 4 months after receiving their last dose of study drug(s).
- 3.2.6 Male patients who intend to donate sperm during the course of this study or 4 months after receiving their last dose of study drug(s).
- 3.2.7 Ongoing toxicities \geq grade 2 from prior therapy, except those related to hydroxyurea (which is permitted through the first 5 days of study treatment).
- 3.2.8 APL (M3).
- 3.2.9 Active central nervous system (CNS) leukemia.
- 3.2.10 History of allergic reactions attributed to compounds of similar chemical or biologic composition to MLN4924 (pevonedistat) or belinostat.
- 3.2.11 Stem cell transplant within previous 3 months prior to initiation of study therapy.
- 3.2.12 Major surgical procedures \leq 28 days before beginning study treatment or minor surgical procedures \leq 7 days before beginning study treatment. No waiting required after placement of a vascular access device.
- 3.2.13 Uncontrolled intercurrent illness or infection.
- 3.2.14 Circulating blast count $>50,000 \text{ mm}^3$ within 7 days preceding enrollment.
- 3.2.15 Current candidacy for a potentially curative allogenic stem cell transplant, unless declined.
- 3.2.16 Left ventricular ejection fraction (LVEF) $<50\%$ as assessed by echocardiogram or radionuclide angiography.
- 3.2.17 Prolongation of the heart-rate corrected QT (QTc) interval $\geq 450 \text{ ms}$ (*i.e.*, grade 1 or higher) on electrocardiogram (ECG) prior to initiation of study treatment.
 - If baseline QTc on screening ECG is $\geq 450 \text{ ms}$ (*i.e.*, grade 1 or higher):
 - Check potassium and magnesium serum levels, and
 - Correct any identified hypokalemia and/or hypomagnesemia and repeat ECG to confirm QTc interval.
 - For patients with baseline heart rate $<60 \text{ bpm}$ or $>100 \text{ bpm}$, manual measurement of QT interval by cardiologist is required, with Fridericia correction applied to that manual measurement to determine the QTc for eligibility consideration.

Note: For patients with a heart rate of 60-100 bpm, manual measurement of QT interval and use of the Fridericia formula to determine QTc is NOT required.

3.2.18 Known cardiopulmonary disease defined as:

- Unstable angina;
- Congestive heart failure (New York Heart Association [NYHA] Class III or IV; see Appendix B);
- Myocardial infarction (MI) within 6 months prior to first dose (patients who had ischemic heart disease such as ACS, MI, and/or revascularization greater than 6 months before screening and who are without cardiac symptoms may enroll);
- Symptomatic cardiomyopathy;
- Clinically significant pulmonary hypertension requiring pharmacologic therapy
- Clinically significant arrhythmia defined as any of the following:
 - History of polymorphic ventricular fibrillation or torsade de pointes
 - Permanent atrial fibrillation (a fib), defined as continuous a fib for ≥ 6 months
 - Persistent a fib, defined as sustaining a fib lasting > 7 days and/or requiring cardioversion in the 4 weeks before screening
 - Grade 3 a fib defined as symptomatic and incompletely controlled medically, or controlled with device (e.g., pace maker), or ablation in the past 6 months
 - Patients with paroxysmal a fib or $<$ Grade 3 a fib for a period of at least 6 months are permitted to enroll provided that their rate is controlled on a stable regimen
 - Known congenital long QT syndrome.
 - Second degree atrioventricular (AV) block type II or third degree AV block
 - Ventricular rate <50 bpm or > 120 bpm.

3.2.19 Treatment with clinically significant metabolic enzyme inducers within 14 days before the first dose of the study drug.

Note: Because the lists of these agents are constantly changing, it is important to regularly consult a frequently-updated medical reference. As part of the enrollment/informed consent procedures, the patient will be counseled on the risk of interactions with other agents, and what to do if new medications need to be prescribed or if the patient is considering a new over-the-counter medicine or herbal product.

3.2.20 Ongoing or planned treatment with strong inhibitors of UGT1A1.

3.2.21 Any known *UGT1A* polymorphism, heterozygous or homozygous.

3.2.22 History of prior therapy with belinostat or MLN4924 (pevonedistat).

3.2.23 Active gastrointestinal (GI) conditions that might predispose to drug intolerance or poor drug absorption.

3.2.24 Known hepatic cirrhosis.

3.2.25 Known moderate to severe chronic obstructive pulmonary disease, interstitial lung disease, and pulmonary fibrosis.

3.2.26 No other prior malignancy is allowed except for the following:

- *In situ* cervical cancer,
- Adequately treated basal cell or squamous cell skin cancer,
- Adequately treated Stage I or II cancer from which the patient is currently in complete remission, and
- Any other cancer from which the patient has been disease-free for at least 1 year.

3.2.27 Medical, psychological, or social condition that, in the opinion of the investigator, may increase the patient's risk, interfere with the patient's participation in the study, or hinder evaluation of study results.

3.2.28 Pregnant or nursing. Women of childbearing potential must have a negative serum pregnancy test performed within 7 days prior to the start of study therapy.

Note: Pregnant women are excluded from this study because MLN4924 (pevonedistat) is a NEDD8 inhibitor with the potential for teratogenic or abortifacient effects and because belinostat may cause teratogenicity and/or embryo-fetal lethality by virtue of targeting actively dividing cells. Because there is an unknown but potential risk for AEs in nursing infants secondary to treatment of the mother with MLN4924 (pevonedistat) or belinostat, breastfeeding should be discontinued if the mother is treated with MLN4924 (pevonedistat)/belinostat.

3.3 Inclusion of Women and Minorities

National Institutes of Health (NIH) policy requires that women and members of minority groups and their subpopulations be included in all NIH-supported biomedical and behavioral research projects involving NIH-defined clinical research unless a clear and compelling rationale and justification establishes to the satisfaction of the funding Institute & Center (IC) Director that inclusion is inappropriate with respect to the health of the subjects or the purpose of the research. Exclusion under other circumstances must be designated by the Director, NIH, upon the recommendation of an IC Director based on a compelling rationale and justification. Cost is not an acceptable reason for exclusion except when the study would duplicate data from other sources. Women of childbearing potential should not be routinely excluded from participation in clinical research. [REDACTED]

Both men and women and members of all races and ethnic groups are eligible for this trial. Every attempt will be made to enter all eligible patients in this protocol to address the study objectives in a population representative of the population treated by the participating institutions.

4. REGISTRATION PROCEDURES

4.1 Investigator and Research Associate Registration with CTEP

Food and Drug Administration (FDA) regulations and National Cancer Institute (NCI) policy require all individuals contributing to NCI-sponsored trials to register and to renew their

registration annually. To register, all individuals must obtain a Cancer Therapy Evaluation Program (CTEP) Identity and Access Management (IAM) account at

██████████ In addition, persons with a registration type of Investigator (IVR), Non-Physician Investigator (NPIVR), or Associate Plus (AP), must complete their annual registration using CTEP’s web-based Registration and Credential Repository (RCR) at ██████████

RCR utilizes five person registration types.

- IVR: MD, DO, or international equivalent,
- NPIVR: advanced practice providers (e.g., NP or PA) or graduate level researchers (e.g., PhD),
- AP: clinical site staff (e.g., RN or CRA) with data entry access to CTSU applications such as the Roster Update Management System (RUMS), OPEN, Rave, acting as a primary site contact, or with consenting privileges,
- Associate (A): other clinical site staff involved in the conduct of NCI-sponsored trials, and
- Associate Basic (AB): individuals (e.g., pharmaceutical company employees) with limited access to NCI-supported systems.

RCR requires the following registration documents:

Documentation Required	IVR	NPIVR	AP	A	AB
FDA Form 1572	✓	✓			
Financial Disclosure Form	✓	✓	✓		
NCI Biosketch (education, training, employment, license, and certification)	✓	✓	✓		
HSP/GCP training	✓	✓	✓		
Agent Shipment Form (if applicable)	✓				
CV (optional)	✓	✓	✓		

An active CTEP-IAM user account and appropriate RCR registration is required to access all CTEP and Cancer Trials Support Unit (CTSU) websites and applications. In addition, IVRs and NPIVRs must list all clinical practice sites and Institutional Review Boards (IRBs) covering their practice sites on the FDA Form 1572 in RCR to allow the following:

- Added to a site roster
- Assigned the treating, credit, consenting, or drug shipment (IVR only) tasks in OPEN
- Act as the site-protocol Principal Investigator on the IRB approval, and

In addition, all investigators act as the Site-Protocol PI, consenting/treating/drug shipment, or as the CI on the DTL must be rostered at the enrolling site with a participating organization (i.e.,

Alliance).

Additional information can be found on the CTEP website at

[REDACTED]

